4.4.2 Prohibited Therapy

Use of the following therapies is prohibited during the study:

- Any concomitant therapy intended for the treatment of solid tumors, either approved by health authorities or experimental, including chemotherapy, radiotherapy (except palliative radiotherapy), hormonal therapy, immunotherapy, biologic therapy, or herbal therapy

Patients with rhabdoid tumor and ATRT may receive local therapy (radiation or surgery) after at least four cycles of atezolizumab with approval of the Medical Monitor.
- Traditional herbal or homeopathic or natural medicines

Ingredients for such medicines have not been fully studied, and their use may result in unanticipated drug-drug interactions that may cause or confound assessment of toxicity.
- Immunostimulatory agents, including but not limited to interferon (IFN)- α , IFN- γ , anti-TNF- α , or IL-2 (prohibited during the study and for 10 weeks after the last dose of atezolizumab)

These agents, in combination with atezolizumab, could potentially increase the risk for autoimmune conditions.
- Immunosuppressive medications, including but not limited to cyclophosphamide, azathioprine, methotrexate, and thalidomide

These agents could potentially alter the activity and the safety of atezolizumab.
- Live vaccines and live attenuated vaccines (prohibited during the study and for 5 months after the last dose of study drug)

Initiation of granulocyte colony-stimulating factors (e.g., granulocyte colony-stimulating factor, granulocyte/macrophage colony-stimulating factor, and/or pegfilgrastim) should be discussed with the Medical Monitor.

Systemic corticosteroids may attenuate potential beneficial immunologic effects of treatment with atezolizumab but may be administered at the discretion of the treating physician after consultation with the Medical Monitor, as described in Section 5.1.1.2.

Patients with ATRT can be receiving concurrent treatment with corticosteroids with approval from the Medical Monitor. Patients must be receiving a stable or decreasing dose for ≥ 5 days prior to the baseline MRI scan and at the time of drug initiation. The Medical Monitor should be informed when steroid doses are increased because of declining patient status.

In clinically indicated emergent situations (i.e., anaphylaxis), corticosteroids may be administered without notifying the Medical Monitor in advance, but the Medical Monitor should be notified within 24 hours of the event. If feasible, alternatives to these agents should be considered. *Systemic steroids used as steroid replacement therapy for adrenal insufficiency are permitted.*

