Patients with pediatric solid tumors, including Hodgkin's and non-Hodgkin's lymphoma, may be enrolled into the study (see Section 4.1 for patient inclusion and exclusion criteria). Each tumor type will be considered a distinct tumor type cohort. An initial response assessment will be performed after a minimum of 10 patients have been enrolled in a tumor type cohort and followed up for approximately 6 months, to determine whether further enrollment is needed within that tumor type cohort (cohort expansion) for additional response assessment. A minimum number of responders will be needed for cohort expansion and advancement to the additional response assessment (see [Table 3](#) for more details). Cohort expansion, including the number of patients needed for the additional response assessment, will also take into account practical considerations (e.g., enrollment feasibility), biomarker analysis, safety profiles, and any other relevant information. The maximum number of patients enrolled in any tumor cohort will be 40.

In addition to the planned efficacy analyses mentioned above, interim PK analyses will also be performed. An initial interim PK analysis will be conducted after the first 5 patients have completed Cycle 1, irrespective of age and tumor type cohort. An additional interim PK analysis will be conducted after 5 patients who are < 6 years old (if available) have completed Cycle 1. Following these analyses, dose modifications may be considered for all patients, if warranted, to match adult exposures and to ensure an optimal safety profile. After a minimum of 20 patients have completed Cycle 1, PK and safety analyses will also be conducted.

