4.5 STUDY ASSESSMENTS

See [Appendix 1](#) and [Appendix 2](#) for the schedules of assessments performed during the study.

Unless otherwise stated, the baseline measurement for any given assessment will be defined as the last value obtained before the first dose of study drug. After treatment initiation, changes from baseline abnormalities should be recorded in patient notes. New or worsened clinically significant abnormalities should be recorded as adverse events on the Adverse Event eCRF. Patients should be assessed for toxicity prior to each dose; dosing will occur only if the clinical assessment and local laboratory test values are acceptable.

If the timing of a protocol-mandated study visit coincides with a holiday and/or weekend that precludes the visit, the visit should be scheduled on the nearest following feasible date, with subsequent visits rescheduled accordingly.

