6.1 DETERMINATION OF SAMPLE SIZE

No formal hypothesis testing is planned in this study.

A minimum of 40 patients will be enrolled in this study across all tumor types. In addition, at least two tumor type cohorts must enroll a minimum of 10 patients. To make a preliminary assessment of the efficacy of the study drug, two response assessments are planned: an initial response assessment and an additional response assessment. Taking into account historical control ORRs for each pediatric tumor type, the minimum number of patients in the initial response assessment and the minimum number of responders needed for cohort expansion and advancement to the additional response assessment were calculated and are presented by tumor type in [Table 3](#). Given the bony nature of osteosarcoma, responses in osteosarcomas do not always result in tumor shrinkage as the extracellular matrix produced by the tumor cells does not always disappear even when the cells die ([Benjamin RS 2015](#)). Thus, for osteosarcoma, CBR instead of objective response was considered in the response assessment. Patients with osteosarcoma are considered to have CBR if they have objective response or stable disease for at least 6 months, as determined by RECIST v1.1.

An initial response assessment will consider any available preclinical data in addition to any early efficacy or safety signals seen in the tumor type cohorts (enrollment may be closed while the response assessments are being conducted). The selection of expansion cohorts for additional response assessment, as well as the number of patients needed for the additional response assessment, will also take into account practical considerations (e.g., enrollment feasibility), biomarker analysis, safety profiles, and any other relevant information. The maximum number of patients per tumor type cohort will be 40. Similar consideration will be given to other rare pediatric tumor types that are enrolled in the study and not included in [Table 3](#).

Table 3 Sample Size and Responder Requirements for Initial Response Assessment

Disease (Relapsed/Refractory)	Historical Control Objective Response Rate (%)	Initial Response Assessment	
		Minimum No. of Patients Enrolled	Minimum No. of Responders Needed for Tumor Type Cohort Expansion
Hepatoblastoma	10%	10	2
Hodgkin's disease	60 ^a	14	10
Wilms tumor	10	10	2
Neuroblastoma	18	10	3
Non-Hodgkin's lymphoma	40 ^a	12	6
High-grade osteosarcoma	20 ^b	10	3
Rhabdomyosarcoma	10	10	2

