Non-rhabdomyosarcoma tissue sarcoma	10	10	2
Ewing sarcoma	10	10	2
Rhabdoid tumor	5	6	1
Atypical teratoid rhabdoid tumor	5	6	1

^a Combination therapy.

^b Clinical benefit response: objective response or stable disease for at least 6 months.

Overall, approximately 100 patients will be enrolled in the study.

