6.6.1 Primary Efficacy Endpoint

The primary endpoints for efficacy are ORR and PFS. For patients with measurable disease or patients with neuroblastoma who have evaluable disease at baseline, an objective response is defined as a complete or partial response on two consecutive occasions ≥ 4 weeks apart, as determined by the investigator using RECIST v1.1 for patients with solid tumors (see [Appendix 6](#)), *mINRC* for patients with neuroblastoma (see [Appendix 3](#)), Revised Response Criteria for Malignant Lymphoma for patients with Hodgkin's lymphoma or non-Hodgkin's lymphoma (see [Appendix 4](#)), and *RANO criteria* (see [Appendix 11](#)) for patients with ATRT.

For patients with non-measurable but evaluable disease at baseline (except *patients with neuroblastoma*), an objective response is defined as a complete response on two consecutive occasions ≥ 4 weeks apart, as determined by the investigator using RECIST v1.1 for patients with solid tumors (see [Appendix 6](#)), Revised Response Criteria for Malignant Lymphoma for patients with Hodgkin's lymphoma or non-Hodgkin's lymphoma (see [Appendix 4](#)), and *RANO criteria* (see [Appendix 11](#)) for patients with ATRT.

ORR is the percentage of patients who are determined to have an objective response. Patients with no post-baseline tumor assessments will be counted as non-responders. ORR and corresponding 95% exact CI using the Blyth–Still–Casella method will be summarized overall and by tumor type cohort (except for the osteosarcoma tumor type cohort).

CBR is defined as objective response or stable disease for at least 6 months, as determined by RECIST v1.1 for patients with osteosarcoma (see [Appendix 6](#)). CBRR is the percentage of patients who are determined to have a CBR. Patients with no post-baseline tumor assessments will be counted as not having CBR. CBRR and corresponding 95% CI will be summarized for the osteosarcoma tumor type cohort only.

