A sum of the diameters (longest for non-nodal lesions, short axis for nodal lesions) for all target lesions will be calculated and reported as the baseline sum of diameters. If lymph nodes are to be included in the sum, then, as noted above, only the short axis is added into the sum. The baseline sum of diameters will be used as a reference to further characterize any objective tumor regression in the measurable dimension of the disease.

All other lesions (or sites of disease), including pathological lymph nodes, should be identified as non-target lesions and should also be recorded at baseline. Measurements are not required and these lesions should be followed as “present,” “absent,” or in rare cases “unequivocal progression.”

In addition, it is possible to record multiple non-target lesions involving the same organ as a single item on the eCRF (e.g., “multiple enlarged pelvic lymph nodes” or “multiple liver metastases”).

RESPONSE CRITERIA

a. Evaluation of Target Lesions

This section provides the definitions of the criteria used to determine objective tumor response for target lesions.

- Complete response (CR): disappearance of all target lesions
Any pathological lymph nodes (whether target or non-target) must have reduction in short axis to < 10 mm.
- Partial response (PR): at least a 30% decrease in the sum of diameters of target lesions, taking as reference the baseline sum of diameters
- Progressive disease (PD): at least a 20% increase in the sum of diameters of target lesions, taking as reference the smallest sum on study (nadir), including baseline
In addition to the relative increase of 20%, the sum must also demonstrate an absolute increase of at least 5 mm.
The appearance of one or more new lesions is also considered progression.
- Stable disease (SD): neither sufficient shrinkage to qualify for PR nor sufficient increase to qualify for PD, taking as reference the smallest sum on study

Appendix 6

Response Evaluation Criteria in Solid Tumors: Modified Excerpt from Original Publication (cont.)

b. Special Notes on the Assessment of Target Lesions

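### No rule says whether a response scored after permitted surgery or radiation counts in the rhabdoid and ATRT cohorts, where one responder meets the expansion minimum

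*Combined protocol and SAP*

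**What the plan says.** - **Local therapy.** Section 4.4.2 states that those who have "rhabdoid tumor and ATRT may receive local therapy (radiation or surgery) after at least four cycles of atezolizumab with approval of the Medical Monitor". No other cohort has this permission, palliative radiotherapy aside. Section 5.1.1.1 allows dosing to be interrupted for surgery, so such a patient can stay on study drug.
- **Response.** Section 6.6.1 says an "objective response is defined as a complete or partial response on two consecutive occasions" at least 4 weeks apart, judged by the investigator. The only stated non-responder rule is for patients with no scan after baseline.
- **Reference point.** Under Section 4.5, "the baseline measurement for any given assessment will be defined as the last value obtained before the first dose of study drug", unless otherwise stated. Appendix 6 defines partial response as "at least a 30% decrease in the sum of diameters of target lesions, taking as reference the baseline sum of diameters".
- **Use of the count.** Table 3 (Section 6.1) has a column headed "Minimum No. of Responders Needed for Tumor Type Cohort Expansion". For rhabdoid tumor and for ATRT the entry is 1, with 6 patients and a historical rate of 5%. Section 3.1 instead places the initial assessment after "a minimum of 10 patients have been enrolled in a tumor type cohort and followed up for approximately 6 months". Section 6.1 adds that expansion also weighs "biomarker analysis, safety profiles, and any other relevant information".

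**The concern.** Neither RECIST nor RANO, as reproduced in the appendices, asks why a lesion shrank or disappeared. If a surgeon removes a target lesion, or radiation shrinks it, while the patient remains on atezolizumab, the response definition can be met without any drug effect. Likewise, a response first seen at week 12 could have its only confirmation on a scan taken after local therapy.

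ORR is a primary efficacy endpoint, and the permission falls exactly where one responder decides whether the minimum is met. The other nine Table 3 cohorts need between 2 and 10. PFS and DOR are exposed too, mainly but not only in the drug's favor, because Sections 6.6.1 and 6.6.2 have no local-therapy provision for either.

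**Working it through.** **1. Does any existing rule cover these scans?** The nearest provisions do not:

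| Provision | What it covers |
|---|---|
| Section 4.4.1, non-interference with target lesions | Palliative radiotherapy only |
| Appendix 6, lesions with prior local treatment, or irradiated within 3 weeks before Cycle 1 | Measurability and target selection at baseline |
| Appendix 6, special notes on target lesions | Nodes, lesions too small to measure, split or merged lesions; not resected ones |
| Appendix 6, missing assessments | Lesions not imaged or not readable |
| Appendix 11, radiation and postoperative change | Calling T2/FLAIR progression; not response |
| Section 4.6.2, tumor follow-up ends at another treatment | Patients already off study drug |

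Medical Monitor approval governs whether local therapy is given, not how later scans are scored.

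**2. Does the timing fit?** Cycles last 3 weeks (Appendix 1), and scans fall in the last week of Cycles 2, 4, 6 and 8 (Section 4.5.5.1).
- Cycle 4 ends on day 4 × 21 = 84 (week 12), the earliest point for local therapy.
- The Cycle 6 scan falls on days 120–126 (week 18) and the Cycle 8 scan on days 162–168 (week 24).
- The gap is 162 − 126 = 36 to 168 − 120 = 48 days, which satisfies the 28-day confirmation.
- Six months is about day 183, so both scans fall inside the window, with about 183 − 168 = 15 days to spare.

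**3. Size of one misattributed response.** 1/6 = 16.7%, which is 3.3 times the 5% historical rate; 1/10 = 10%, twice that rate.

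**4. Chance of meeting the minimum with no local-therapy responses.** The plan states no error rate or target rate, so there is no figure of its own to reproduce. At a true ORR of 5%, P(at least 1) = 1 − 0.95^n:
- n = 6: 1 − 0.95^6 = 0.265
- n = 10: 1 − 0.95^10 = 0.401

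**5. Illustration with local-therapy responses.** The documents give no frequency. Assume each patient independently has probability q of a confirmed response caused by local therapy. With a 5% drug response rate, P = 1 − [0.95(1 − q)]^n. With an inactive drug, P = 1 − (1 − q)^n.

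| q (assumed) | 5% ORR, n = 6 | 5% ORR, n = 10 | Inactive, n = 6 | Inactive, n = 10 |
|---|---|---|---|---|
| 0 | 0.265 | 0.401 | 0 | 0 |
| 0.02 | 0.349 | 0.511 | 0.114 | 0.183 |
| 0.05 | 0.460 | 0.642 | 0.265 | 0.401 |
| 0.10 | 0.609 | 0.791 | 0.469 | 0.651 |

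These are chances of meeting the minimum, not of expanding the cohort.

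**The case against.** **The decision is not mechanical.** No formal testing is planned, Section 6.8.2 calls the study hypothesis-generating, other information is weighed, stopping enrollment is optional (Section 3.1.2), and the iDMC may contribute (Section 3.1.4). The Medical Monitor approves each local therapy, so the sponsor would know of every affected case. This stands, and it limits the consequence. It does not say whether the response counts in the ORR or toward the minimum.

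**An investigator would not score it that way.** The Appendix 6 convention that locally treated lesions are generally not measurable points in that direction. In ATRT, RANO also requires no new lesions, stable or better T2/FLAIR findings and clinical status, and steroid limits. These conditions lower the chance. The convention, however, is written for baseline, and the RANO conditions can hold after successful surgery. Patients with synchronous rhabdoid tumor and ATRT are scored by RECIST (Section 4.5.5.2), without the RANO steroid and clinical-status conditions.

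**The frequency is assumed.** This is correct. On scheduled scans a patient must complete four cycles, be approved, be treated before week 18, and show response at weeks 18 and 24. Anticipated major surgery is an exclusion (Section 4.1.2), and delays can push the second scan past 6 months. Only 0.265 and 0.401 rest on document figures, and those are the values without the problem.

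**The remedy creates the opposite error.** A true drug response first seen at week 12, followed by local therapy, would become a non-response, and 1/6 could become 0/6. This is a real cost, and it is why such patients need separate listing and an all-assessments analysis beside the main one.

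**Conclusion.** The concern holds. The omission is clear from the text, and the stated responder rule, followed literally, allows one surgically or radiation-induced response to meet the minimum in either cohort. The firm size is 1/6 (16.7%) or 1/10 (10%) against 5%. Any shift in the chance of meeting the minimum depends on the assumed q: at a 5% drug response rate and n = 6 it runs from no change at q = 0 to 0.609 at q = 0.10. Because expansion is a judgment and q may be near zero, this is a point the sponsor should fix rather than one that undermines the trial. It is best settled in advance, since otherwise the handling of a single known patient would be decided case by case in an open-label study.

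**What to change.** In Section 6.6.1, and for the Table 3 count in these two cohorts:

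- Base the main ORR on assessments up to the last scan before any on-study local therapy to the tumor. Count a response only if it is first documented and confirmed by then. Keep all other patients in the denominator as non-responders.
- List separately (a) responses seen before local therapy but confirmed only after it, and (b) responses first seen afterward, noting whether they are in untreated lesions.
- Report the all-assessments ORR as a sensitivity analysis.
- Keep the current PFS and DOR rules as the main analysis, and add a sensitivity analysis censoring at the last assessment before local therapy. That censoring may be informative, so it should not be the main analysis.
- Check that the eCRF, which is not among the documents, captures the date and site of local therapy.
- Reconcile the minimum of 6 in Table 3 with the minimum of 10 in Section 3.1.

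The clinical permission for local therapy is not altered. The work is modest: analysis wording, two listings and the sensitivity analyses. The statistical cost is that genuine late responses, which Appendix 5 anticipates, may leave the main ORR. For local therapy given right after week 12, only a response seen at week 6 and confirmed at week 12 would count on scheduled scans. The listings and the all-assessments analysis keep the rest visible.

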4.5 STUDY ASSESSMENTS

See [Appendix 1](#) and [Appendix 2](#) for the schedules of assessments performed during the study.

Unless otherwise stated, the baseline measurement for any given assessment will be defined as the last value obtained before the first dose of study drug. After treatment initiation, changes from baseline abnormalities should be recorded in patient notes. New or worsened clinically significant abnormalities should be recorded as adverse events on the Adverse Event eCRF. Patients should be assessed for toxicity prior to each dose; dosing will occur only if the clinical assessment and local laboratory test values are acceptable.

If the timing of a protocol-mandated study visit coincides with a holiday and/or weekend that precludes the visit, the visit should be scheduled on the nearest following feasible date, with subsequent visits rescheduled accordingly.

4.5.1 Informed Consent Forms and Screening Log

Written informed consent, and assent when applicable, for participation in the study must be obtained before performing any study-specific screening tests or evaluations. Informed Consent Forms and Child's Informed Assent Forms for enrolled patients and for patients who are not subsequently enrolled will be maintained at the study site.

All screening evaluations must be completed and reviewed to confirm that patients meet all eligibility criteria before enrollment. The investigator will maintain a screening log to record details of all patients screened and to confirm eligibility or record reasons for screening failure, as applicable.

4.5.2 Medical History and Demographic Data

Medical history includes clinically significant diseases, surgeries, cancer history (including prior cancer therapies, current cancer stage, and procedures), menstrual history, fertility history, and puberty history. In addition, all medications (e.g., prescription drugs, over-the-counter drugs, herbal or homeopathic remedies,

nutritional supplements) used by the patient within 7 days prior to initiation of study drug will be recorded.

Demographic data will include age, sex, and self-reported race/ethnicity as permitted by local regulatory authorities.

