3.4 OUTCOME MEASURES

3.4.1 Safety Outcome Measures

The safety outcome measures for this study are as follows:

- Nature, frequency, severity, and timing of adverse events, including serious adverse events and adverse events of special interest
- Changes in vital signs, physical findings, and clinical laboratory test results during and following administration of atezolizumab
- Growth patterns (relative to age-specific standards for height and weight)
- Development patterns (relative to onset of menarche [for females] and pubertal changes)
- Change in tetanus toxoid antibody titers at study discontinuation as compared with pretreatment values

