4.5.3 Physical Examinations and Assessments

A complete physical examination should include an evaluation of the head, eyes, ears, nose, and throat and the cardiovascular, dermatological, musculoskeletal, respiratory, gastrointestinal, genitourinary, and neurological systems. Any abnormality identified at baseline should be recorded on the General Medical History and Baseline Conditions eCRF.

The Lansky Performance Status should be performed for patients who are < 16 years old, and the Karnofsky Performance Status should be performed for patients who are ≥ 16 years old.

At subsequent visits (or as clinically indicated), changes from baseline abnormalities should be recorded in patient notes. New or worsened clinically significant abnormalities should be recorded as adverse events on the Adverse Event eCRF.

Fractional shortening or LVEF should be determined within 28 days prior to initiation of study drug by either echocardiography or MUGA scan.

During the treatment period, weight will be measured at the beginning of each cycle. During the follow-up period, weight should be measured every 3 months for the first 2 years, every 6 months during the 3rd year, and yearly thereafter.

During the treatment period, height, head circumference (until the age of 3 years), and Tanner stage should be measured every four cycles (approximately every 3 months). During the follow-up period, height, head circumference, and Tanner stage should be measured every 3 months for the first 2 years, every 6 months during the 3rd year, and yearly thereafter. Tanner staging should be performed until the patient has reached Tanner Stage V.

4.5.3.1 *Neurologic Examinations (ATRT Only)*

For patients with ATRT, a complete neurologic examination should be completed at every patient visit, including at baseline (see Schedule of Assessments in [Appendix 1](#)). Any abnormality identified at baseline should be recorded on the General Medical History and Baseline Conditions eCRF.

At subsequent visits (or as clinically indicated), changes from baseline abnormalities need to be reviewed carefully prior to administering the next atezolizumab dose.

Atezolizumab should not be administered if there is any sign of increased intracranial pressure.

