4.5.6 Laboratory, Biomarker, and Other Biological Samples

Assessments that require blood draws should be monitored closely to ensure that institutional guidance regarding total blood volume taken for samples is maintained. In situations where no institutional guidance is available, no more than 2.5% of the total blood volume should be taken at one time and no more than 5% of the total blood volume should be taken over a 30-day period (total blood volume is defined as 80 mL/kg). Institutions should use micro-sampling systems to minimize the amount of blood drawn when able. In situations where the total amount will exceed the amount stated above, clinical laboratory assessments should be prioritized. Any remaining blood should be sent for PK analysis and immunogenicity followed by biomarker and PD analyses.

Laboratory tests results must meet the inclusion criteria and not meet the exclusion criteria at the time of screening. If laboratory tests are performed again prior to the first dose, they must continue to meet the inclusion criteria and not meet the exclusion criteria.

Samples for the following laboratory tests will be sent to the study site's local laboratory for analysis:

- Hematology (WBC count, hemoglobin, platelet count, 3-cell differential count [absolute neutrophils, monocytes, and lymphocytes])
- Serum chemistry (sodium, potassium, magnesium, chloride, bicarbonate, glucose, BUN or urea, creatinine, total protein, albumin, phosphorus, calcium, total bilirubin [if abnormal, fractionate sample for direct and indirect], alkaline phosphatase, ALT, AST, LDH, amylase, and lipase)
- Creatinine clearance should be done as clinically indicated. If radioisotope glomerular filtration rate is routinely performed at the institution to measure patients' creatinine clearance, this test can be used to assess renal function at screening, per the eligibility criteria. Otherwise, serum creatinine is sufficient to document renal function at screening.
- Coagulation panel (INR, aPTT, PT)
- Urinalysis (specific gravity, glucose, protein, blood) in children who are >3 years of age
- Pregnancy test

All patients of childbearing potential will undergo a serum pregnancy test at screening (prior to Cycle 1) within 1 week prior to initial dose. Urine or serum pregnancy test will be performed prior to all subsequent cycles.

- Thyroid function testing (thyroid-stimulating hormone, free T3, free T4)

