Appendix 1 Schedule of Assessments

Day	Screening Period ^a	Treatment Period															Follow-Up Period ^b		
		C1			C2		C3	C4	C5	C6	C7	C8	C9	C10	C11	C12+	Study Drug Discont. ^c	Day 90 Follow-Up ^c	Long-Term Follow-Up ^d
	-28 to -1	1	8	15	1	ATRT Only		1	1	1	1	1	1	1	1	1			
						8	15												
Informed consent ^a	x																		
Archival or fresh tumor tissue ^e	x																		
Medical history and demographics ^f	x																		
Echocardiogram or MUGA	x																		
Serum or urine pregnancy test ^g	x				x			x	x	x	x	x	x	x	x	x			
Vital signs ^h	x	x	x	x	x	x	x	x	x	x	x	x	x	x	x	x	x	x	
Physical examination ⁱ	x	x	x	x	x	x	x	x	x	x	x	x	x	x	x	x	x	x	
Weight ^j	x	x			x			x	x	x	x	x	x	x	x	x	x	x	x
Height, head circumference, Tanner staging ^k	x								x				x				x	x	x
Lansky or Karnofsky Performance Status ^l	x	x	x	x	x	x	x	x	x	x	x	x	x	x	x	x	x	x	
Hematology ^{m,n}	x	x	x	x	x			x	x	x	x	x	x		x		x	x	
Chemistry ^{n,o}	x	x	x	x	x			x	x	x	x	x	x		x		x	x	
Urinalysis ^{n,p}	x	x			x			x	x		x		x		x		x	x	

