Appendix 1 Schedule of Assessments (cont.)

-
- ^c Patients who discontinue study drug should return to the clinic for study drug discontinuation visits within 28 days of the last dose of atezolizumab. This may be done at the clinical visit where clinical or radiographic progression is first noted). A follow-up visit should also be done 90 (\pm 10) days after the last dose of study drug. If treatment with another anti-cancer treatment is scheduled to begin within 90 days after the last dose of study drug, this visit should be performed before the patient starts the other treatment, if possible. *If the day 90 visit is done after initiation of another anti-cancer treatment, only PK and/or ATA blood samples and those laboratory tests needed to monitor for the resolution of adverse events need to be drawn.*
- ^d Long-term follow-up information will be collected every 3 months during the first two years (Years 1 and 2), every 6 months during Year 3, and yearly until study termination by Sponsor, death, loss to follow-up, or withdrawal of consent, whichever occurs first.
- ^e A tumor specimen and associated pathology report must be confirmed to be available prior to patient participation in any study-specific screening procedures and must be shipped within 30 days of first dosing. See Section 4.5.6 for details on sample collection.
- ^f Medical history includes clinically significant diseases, surgeries, cancer history (including prior cancer therapies, current cancer stage, and procedures), menstrual history, fertility history, and puberty history. Demographic data will include age, sex, and self-reported race/ethnicity as permitted by local regulatory authorities.
- ^g All females of childbearing potential must undergo a serum pregnancy test within one week of the initial dose. Urine or serum pregnancy tests must be performed prior to the start of all subsequent cycles.

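### Onset of menarche is named as part of a safety outcome, but the protocol requires no menarche record after screening for girls who are premenarchal at entry

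*Combined protocol and SAP*

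**What the plan says.** Section 3.4.1 lists five safety outcome bullets. The fourth is "Development patterns (relative to onset of menarche [for females] and pubertal changes", and the synopsis carries the same item. Menarche and pubertal changes appear as two separate reference points.

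Collection is described in three places:

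- Section 4.5.2 puts "menstrual history, fertility history, and puberty history" inside medical history. Footnote f of Appendix 1 repeats this for the row "Medical history and demographics", and that row carries a single mark, at screening.
- Section 4.5.3 covers the treatment period: "During the treatment period, height, head circumference (until the age of 3 years), and Tanner stage should be measured every four cycles". For follow-up it says "Tanner stage should be measured every 3 months for the first 2 years, every 6 months during the 3rd year, and yearly thereafter". Tanner staging ends at Stage V. Footnote k of Appendix 1 gives the same schedule and ends height measurement at that stage too.
- Section 6.3, the safety analysis section, covers exposure, adverse events, deaths and laboratory toxicities. It has no line on growth, Tanner stage or menarche.

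A related strand runs through Section 4.1.1 (contraception agreement at entry), Section 4.5.6 and footnote g of Appendix 1 (pregnancy tests). All of these apply to patients of childbearing potential, for example "All patients of childbearing potential will undergo a serum pregnancy test at screening", with further tests before each later cycle.

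**The concern.** A named outcome needs a step that generates its data. Here the history that would hold menarche is taken once, before the first dose. The repeated assessment is a different measurement: a Tanner stage does not say whether menarche has occurred, or when.

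Eligibility runs from birth to under 30 years (Section 3.1), and Section 3.3.2 expects most patients to be under 18. The study can stay open until 5 years after the last patient is enrolled (Section 3.2). Menarche during observation is therefore foreseeable. A missing analysis rule can be written later, but a date that was never asked for cannot be supplied at analysis. If the plan is followed exactly, the only menarche onsets it requires to be recorded are those that happened before exposure.

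**Working it through.** The plan states no figure on this point, so the check sets the outcome beside each place where data for it could arise.

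1. **Outcome.** The synopsis and Section 3.4.1 name two elements: onset of menarche (girls) and pubertal changes.
2. **Screening.** Menstrual and puberty history is taken (Section 4.5.2; Appendix 1 footnote f). This covers menarche for girls already past it at entry.
3. **On treatment.** The pubertal item is Tanner stage (Section 4.5.3; footnote k). With 3-week cycles, the interval is 4 × 21 = 84 days, which agrees with the protocol's own gloss: "Tanner stage should be measured every four cycles (approximately every 3 months". Menarche and menstrual status are not mentioned.
4. **Follow-up.** Tanner stage continues at 3-monthly, then 6-monthly, then yearly visits, until Stage V. Menarche is again not mentioned.
5. **Other routes.** Physical examinations include the genitourinary system, but after baseline the examination text calls for changes from baseline abnormalities in the patient notes and new or worsened clinically significant abnormalities as adverse events. Normal menarche is neither.
6. **Analysis.** Section 6.3 has no development summary, and the list of safety assessments in Section 3.1 has no development item.

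Matching outcome to data:

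| Element | Girls past menarche at entry | Girls premenarchal at entry |
|---|---|---|
| Pubertal changes | Tanner stage | Tanner stage |
| Onset of menarche | Screening history | No required record |

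One cell of the four is empty, and it is the only one that could hold an onset after exposure.

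**Childbearing potential.** The contraception agreement is an entry criterion (Section 4.1.1). The pregnancy tests (Section 4.5.6; footnote g) apply to whoever has the status. The documents neither define the status nor say when, after entry, it is determined again.

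**The case against.** Several points can fairly be made against this.

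- **The outcome can still be reported.** A reader might infer that the whole development outcome is lost. The documents do not support that. Tanner stage is collected at baseline, on treatment and in follow-up for both sexes, so pubertal changes can be described.
- **Menarche may be meant as a reference point.** The neighbouring bullet on growth uses the same construction for age standards. On that reading the screening history serves girls past menarche at entry. It does not help girls who are premenarchal at entry, because even a reference point has to be observed.
- **The eCRF may hold a menarche field.** It is not among the documents, and the grey shading that marks items not entered on it is lost in the text. This objection stands: the point is about what the protocol text requires, and no capture rate can be stated.
- **Investigators will notice.** They see patients every cycle and ask about changes in health. That is discretion, and across about 50 sites it is not a basis for consistent dates.
- **A single-arm study could not isolate a drug effect on menarche anyway.** True. The study plans no formal hypothesis testing, so the data would be descriptive. That limits the importance of the gap but does not explain naming the item without collecting it.
- **Pregnancy testing.** A reader might infer that a girl who matures on treatment falls outside the testing rule. She does not. The rule follows status, so she comes under it once she has that status. All that can be said is that no re-check of the status is written. The consent pages were removed before review, so what families are told cannot be judged.

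**Conclusion.** The point holds in a narrow form. On-study onset of menarche, one component of one of five safety outcome bullets, has no required collection for girls premenarchal at entry, and no summary of development is planned. The number of girls affected cannot be derived from the documents: they give neither the expected sex and age distribution nor the expected length of observation per patient.

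The conclusion rests on reading the single screening mark for medical history as complete, and on the eCRF following the protocol text. It is a minor point, worth acting on because the remedy is cheap and the data cannot be recovered afterwards.

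On childbearing potential, the finding is limited to this: the contraception and pregnancy-test passages depend on a status that the protocol does not say is re-checked during the study.

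**What to change.** - In Section 4.5.3 and footnote k of Appendix 1, add menarche status and date, for girls premenarchal at their last assessment, to the existing Tanner and height visits, on treatment and in follow-up.
- State that the question continues until menarche is recorded, even if Tanner staging has stopped at Stage V. The weight and long-term follow-up visits continue, so a visit is still available.
- Add a descriptive summary of development (Tanner stage and menarche) to Section 6.3.
- Ask the sponsor to reconcile Sections 4.1.1 and 4.5.6 and footnote g of Appendix 1 on how and when childbearing potential is determined during the study. No clinical rule is proposed here.

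The cost is one eCRF question at visits already scheduled and one descriptive summary, with no new visit or procedure.
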